An important non-pharmacologic intervention for SCD is RBC transfusion.³ RBC transfusions are indicated for severe symptomatic anemia, acute complications like stroke or acute multi-organ failure, and/or secondary prevention of stroke or recurrent pain crises in individuals with SCD.³ The two primary types of RBC transfusions, simple (addition of RBCs without removal of the patient's blood) and exchange (removal of the patient's blood and replacement with donor packed RBCs), have both acute and chronic indications. Treatment guidelines recommend acute transfusions for symptomatic anemia, ACS, multiorgan failure, and preoperatively; chronic transfusions, usually administered monthly,

are recommended for stroke prevention.³ While blood transfusions can improve SCD complications, they are also associated with important risks that can occur at each transfusion: resultant iron overload can lead to end organ damage, alloimmunization can lead to delayed hemolytic transfusion reactions (DHTR) and mortality, and transfusion transmitted infections can cause organ damage and mortality.^{3,8–11} Additionally, transfusion administration can be burdensome to patients due to the need for frequent venous access, which can cause pain, psychological distress, and interruptions to daily life.¹² A significant unmet need exists for new therapies and interventions that address the clinical complications of SCD while mitigating the patient burden.

Once-daily oral administration of voxelotor has been shown to reduce red-cell sickling, blood viscosity and improve red-cell deformability in vitro and to extend red-cell half-life and reduce anemia and hemolysis in vivo. ¹³ Evidence from clinical studies has demonstrated that voxelotor has a beneficial effect on Hb levels, a critical factor in the decision for an RBC transfusion. However, no clinical trials have demonstrated the impact of voxelotor on rates of RBC transfusion. While preliminary real-world evidence (RWE) supports a reduction in RBC transfusions associated with voxelotor use, these studies are limited by small sample sizes and lack of comparator populations. ^{14,15}

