Iron chelation use	Baseline Characteristic; Covariate	[Baseline]	Frequency and proportion (N, %)
Delayed hemolytic transfusion reactions	Baseline Characteristic; Covariate	[Baseline]	Frequency and proportion (N, %)
Alloimmunization	Baseline Characteristic; Covariate	[Baseline]	Frequency and proportion (N, %)
Death	Baseline Characteristic; Covariate	[Follow-up]	Frequency and proportion (N, %)
Voxelotor discontinuation	Baseline Characteristic; Covariate	[Follow-up]	Frequency and proportion (N, %)

Abbreviations: ESA: Erythropoietin Stimulating Agent; RBC: Red blood cell; SCD: Sickle cell disease.

Baseline genotype will not be included in the PS model because patients commonly have multiple values due to coding/billing errors and this value is more likely to be misclassified. The most frequently occurring value (not including unknown/other) will be selected

- 2. SCD-specific comorbidities include the following: acute chest syndrome, acute coronary syndrome, acute osteomyelitis, acute renal failure, aplastic crisis, intracerebral and subarachnoid hemorrhage, myocardial infarction, priapism, splenic sequestration crisis, transfusion-associated reaction, venous thromboembolism, avascular necrosis, cholelithiasis, chronic kidney disease, chronic pain, diabetes, heart failure, iron overload, leg ulcer, pulmonary hypertension, VOC, and retinopathy.
- 6. Given feasibility analyses have indicated a low proportion of patients (<25%) have lab values, Hb will be excluded from the PS model. Hb will be evaluated excluding those measurements within 2 days of an acute event or within 30-60 days of a transfusion event. Full algorithm will be provided in a separate statistical analysis plan.
- 4. CCI categories include: myocardial infarction, congestive heart failure, peripheral vascular disease, cerebrovascular disease, dementia, chronic pulmonary disease, rheumatic disease, peptic ulcer disease, mild liver disease, diabetes without chronic complication, diabetes with chronic complication, hemiplegia or paraplegia, renal disease (mild to moderate), renal disease (severe), any malignancy without metastasis including leukemia and lymphoma, moderate or severe liver disease, metastatic solid tumor, human immunodeficiency virus, acquired immunodeficiency syndrome

The table above includes a summary of baseline characteristics and possible covariates for PS modeling. Covariates will be selected using the diagnostic criteria outlined in the data analysis plan (Section 9.7).

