Required 1-year minimum follow-up	Two subgroup analyses have been proposed to evaluate bias introduced by differential follow-up. First, a subgroup analysis of patients with a minimum of 1-year of follow-up will be performed to evaluate the impact of informative censoring.	To address the impact of informative censoring and differential follow-up
Matched censoring	If meaningful differences in follow-up time are observed, matched censoring will be performed to assess the impact of differential follow-up between the exposed and referent group for the primary objective. Bias due to differential follow-up can arise when the reasons for participants dropping out or being lost to follow-up are related to both the treatment and the outcome. Matched censoring mitigates this bias by censoring all patients within a matched set (i.e., patients that have been matched by PS matching) at the earliest time in which a patient in the set was censored. In the context of 1:2 PS matching, where each exposed patient is matched to two referent patients, the matched set will consist of at most three individuals. Thus, matched censoring in this scenario involves censoring data for all three individuals in a matched set at the earliest observed censoring time among them.	To address the impact of informative censoring and differential follow-up
Stratification by number of RBC transfusions in baseline	The number of RBC transfusions PPPY in baseline will be categorized and the primary objective will be reported separately for those categories. This analysis will be performed for all objectives.	To understand the effect of the treatment on high-risk subgroups.
Subgroup analysis by Hb level	The primary analysis will also be performed on a subgroup of patients with Hb values at baseline. A separate PS model will be utilized for this subgroup.	To understand the effect of the treatment on high-risk subgroups and patients with available baseline data.
Subgroup analysis by prior medications	A subgroup analysis will be performed on patients who received hydroxyurea, crizanlizumab, L-glutamine, and/or ESA in baseline the exposed and referent groups.	To understand the effect of other SCD treatments.

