Because this study does not include an active comparator as a control group, CEM will be used to select the index date of matched controls on the initiation of voxelotor for exposed patients. All exposed patients will be selected prior to controls to preserve sample size. Sampling bias may be introduced by prioritizing exposures, but the impact is limited due to a larger pool of untreated control patients than potential exposures. There may be differences in patient characteristics dependent on when patients enter the study population (i.e., initiating voxelotor versus periods without treatment for matched controls). However, PS methods will be utilized to control for observed baseline confounding between the exposed and referent groups. Linked Ouest data will be used to evaluate Hb levels in baseline (an important diagnostic criterion for RBC transfusions). Feasibility analyses will be conducted prior to implementation to assess the number of patients in this study with available Hb data. Assuming a significant number of patients will not have Hb data in baseline, a sensitivity analysis has been proposed to assess the primary outcome among patients with this lab data. However, there may be differences in the frequency of Hb testing between the exposed and control group, relative to when patients enter the study cohort. For most subgroup analyses, the PS obtained from the overall study cohort PS model will be used for PS adjustment. However, for the subgroup of patients with non-missing Hb values in baseline, the PS model will be re-fit and will include an additional covariate (mean Hb value). Depending on the utilization of other SOC treatments in both the exposed and control groups, other subgroup analyses may be conducted. Additionally, the primary analysis will be as-treated, which includes discontinuation of voxelotor as a censoring criterion in the exposed group. This creates potential for confounding via differential censoring between the exposed and referent groups. However, to account for these potential differences in follow-up time, matched censoring will be used to censor matched controls on the date of their voxelotor match's discontinuation date as a sensitivity analysis.

A summary of the potential limitations of the RWD in this study and the mitigation strategies that will be applied is provided in Annex Table 3.

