Hb labs	Missingness	Based on preliminary data explorations, approximately 17% of patients have at least one Hb result during the study timeframe. All lab values have an associated date and time.	Due to missingness in Hb lab results, Hb cannot be adjusted for in the primary analysis; however, a sensitivity analysis is planned that will stratify by baseline Hb and a separate propensity score model will be used to adjust for Hb results.

SCD genotype	Missingness	It is more likely severe genotypes (e.g., HbSS) should be requiring more than 2 RBC transfusions in the past year.	RBC transfusion by SCD genotype will be assessed in sensitivity analysis.
		Based on preliminary data explorations, approximately 93% have patients have genotype documented in our data set.	
Comorbidities	Missingness	There is a possibility of missing information for patients is expected to be low but possible if patients seek healthcare without the use of medical or pharmacy insurance.	Continuous enrollment in a health plan is required as part of the analysis. Thus, all healthcare interactions through insurance will be captured and including documented comorbidities recorded in medical billing records. If missingness occurred, no theoretical basis for differential documentation between exposed/unexposed groups exists. Propensity score adjustment aggregates the probability of exposure to voxelotor. It is expected that more severe diseases that would have a larger impact on outcomes would be better captured in the data ² and that limited underreporting of non-severe comorbidities should not have a substantial impact on the overall results.
Treatment adherence	Missingness	These data are not missing. Komodo data has near 100% of patients' pharmacy claims when requiring patients to have continuous enrollment in the pharmacy benefit. For exposed patients, we have 100% of the voxelotor claims through the use of Claritas data.	including as-treated and intent- to-treat analysis to ensure consistent results that best represent a RCT.
Race/ethnicity	Unmeasured confounder	Based on preliminary data explorations, approximately 90% of SCD patients have documented race/ethnicity in our data set. CDC estimates more than 90% are non-Hispanic Black or African American, and an estimated 3%–9% are Hispanic or Latino.	and is not missing from our data set.

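### The Hb subgroup changes the population and adds Hb to the propensity model at the same time, and its transfusion wash-out under-represents frequently transfused patients, so it does not isolate what Hb adjustment does to the primary estimate

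*Protocol*

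**What the plan says.** Section 9.3 (Table 4 footnote on Hb) removes Hb from the main model: "Given feasibility analyses have indicated a low proportion of patients (<25%) have lab values, Hb will be excluded from the PS model". Annex Table 3 gives availability as "approximately 17% of patients have at least one Hb result during the study timeframe" and concludes: "Due to missingness in Hb lab results, Hb cannot be adjusted for in the primary analysis".

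The replacement is a subgroup analysis. Table 7 in Section 9.7.3 says: "The primary analysis will also be performed on a subgroup of patients with Hb values at baseline", with a separate PS model. Section 9.9 adds that "for the subgroup of patients with non-missing Hb values in baseline, the PS model will be re-fit and will include an additional covariate (mean Hb", whereas most other subgroups use the PS from the overall cohort.

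Which Hb values count is set in the same Table 4 footnote: "Hb will be evaluated excluding those measurements within 2 days of an acute event or within 30-60 days of a transfusion event". The window is a range, and the text does not say whether it runs after a transfusion or on both sides. The footnote continues: "Full algorithm will be provided in a separate statistical analysis plan". The Hb value entry in Annex Table 1 asks only for a LOINC code and a numeric result and mentions no wash-out.

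Two other provisions matter. Table 2 requires at least two RBC transfusions in the baseline year. The primary endpoint in Section 9.7.3 is the follow-up transfusion rate minus the baseline rate.

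**The concern.** Section 9.9 calls Hb a possibly important confounder, and Section 9.9 and Annex Table 3 offer this subgroup as the way to deal with it. Anyone using the result will set the subgroup estimate beside the primary estimate and ask whether adjusting for Hb changes the answer.

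As planned, that comparison changes two things together: who is analyzed, and whether Hb is in the PS model. The first change is not neutral. The more often a patient is transfused, the fewer days in the baseline year can yield a usable Hb value, and baseline transfusion frequency is the quantity subtracted in the primary endpoint. A different subgroup estimate could come from losing frequently transfused patients. A similar one could arise from a population shift and an Hb effect that offset each other. The protocol describes no fit without Hb in the same patients. Section 9.9 acknowledges that Hb testing frequency may differ by arm but does not mention selection by transfusion frequency.

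**Working it through.** The protocol states no figure for the effect of the wash-out, so there is none to reproduce. The steps below check its direction and likely size.

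**Step 1: eligible days.** Inputs: a 365-day baseline, k transfusions (at least 2, Table 2), window w = 30 or 60 days (Table 4 footnote). Assumptions: even spacing with the first transfusion on the first baseline day, window after the transfusion only, transfusion day included. Eligible days = max(0, 365 − k(w + 1)).

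| k per year | w = 30 | w = 60 |
|---|---|---|
| 2 | 365 − 62 = 303 | 365 − 122 = 243 |
| 4 | 365 − 124 = 241 | 365 − 244 = 121 |
| 6 | 365 − 186 = 179 | 0 |
| 12 | 0 | 0 |

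Section 7 describes "chronic transfusions, usually administered monthly", which is the last row. Leaving out the transfusion day itself gives 365 − 360 = 5 days (about 1%) at w = 30, so essentially none either way.

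**Step 2: irregular timing.** Simulated chance that at least one of two Hb tests on random days qualifies, with transfusions on random days (30-day / 60-day window):

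| k per year | after only | both sides |
|---|---|---|
| 2 | 0.97 / 0.92 | 0.91 / 0.72 |
| 6 | 0.84 / 0.60 | 0.57 / 0.21 |
| 12 | 0.59 / 0.28 | 0.22 / 0.03 |

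Retention falls with frequency in every scenario, but it is not zero when timing is irregular.

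**Step 3: possible shift in the estimate.** All of this is assumed: a share p of the cohort has 12 transfusions a year, the rest average 2.8, and the effect is proportional to baseline and averages 1.0 in the full cohort. There are four random Hb tests and an after-only window. Simulated retention of monthly patients is 16% (60 days) or 21% (30 days) if evenly spaced, and 49% or 84% if random. Retention of the rest is 97% (60 days) or about 100% (30 days).

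For p = 25%, even spacing, 60 days:
- full-cohort mean = 0.25 × 12 + 0.75 × 2.8 = 5.1
- retained monthly share = (0.25 × 0.16) / (0.25 × 0.16 + 0.75 × 0.97) = 5.2%
- subgroup mean = 2.8 + 9.2 × 0.052 = 3.28
- expected effect = 3.28 / 5.1 = 0.64, a shift of 36%

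For p = 5%, the full-cohort mean is 0.05 × 12 + 0.95 × 2.8 = 3.26. The same steps give:

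| p | even, 60 d | even, 30 d | random, 60 d | random, 30 d |
|---|---|---|---|---|
| 25% | 0.64 | 0.67 | 0.81 | 0.94 |
| 5% | 0.88 | 0.89 | 0.93 | 0.98 |

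The range is therefore about 2-36%. The even-spacing figures count days before the first baseline transfusion as clean. If regular monthly patients are lost completely, as in Step 1, the limits are 1 − 2.8/3.26 = 14% and 1 − 2.8/5.1 = 45%.

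**Step 4: precision of the subgroup.** Section 9.5 gives 185 treated, 1:2 matching, SD 3.0 and an inflation factor of 1.65. SE = √[9 × 1.65 × (1/n + 1/(2n))] = √(22.275/n). At n = 185 this is 0.347, and power for a 1-unit difference is 82% (two-sided 5%, assumed), close to the stated 80%. With Hb in 17-25% of patients, n = 31-46 treated, so SE = √(22.275/31) = 0.85 to √(22.275/46) = 0.70. Power is then about 22-30%.

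**The case against.** The strongest defense has five parts.

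- **No comparison is stated.** Table 7 and Section 9.9 say only that the analysis is run in this subgroup; no rule contrasts it with the full cohort. That is true, but Annex Table 3 presents the analysis as the answer to missing Hb adjustment, and it can serve that purpose only through such a comparison.
- **Selection is on a pre-index covariate.** A reader might infer that missingness is driven by the outcome and that the subgroup estimate is biased. The documents do not support that. Baseline transfusion count is measured before index and is eligible for the PS model. Selecting on it changes the target population and does not by itself bias the treated-versus-control contrast within the subgroup. Table 7 also stratifies the primary objective by baseline transfusion number.
- **Details are left to the SAP.** Window length, direction and entry rule are not final, and Annex Table 1 has no wash-out. This stands, and it makes the selection argument conditional. The lack of a fit without Hb in the same patients remains a gap in the analysis the protocol describes.
- **Few patients may be on monthly transfusion.** Patients with baseline stroke are excluded, and Section 9.9 expects unidentified primary-prevention patients to be few. Nothing in the protocol supports a share as high as 25%.
- **Low availability is the tighter limit, and it is disclosed.** This also stands. Even the larger assumed shifts are within one standard error. But low availability is itself a reason why subgroup and full cohort are not directly comparable.

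A reader might also see a contradiction with Table 7's rationale about high-risk subgroups. That rationale goes on to name patients with available baseline data, and risk in an analysis by Hb level need not mean a high transfusion count.

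**Conclusion.** The point holds in a limited form. The Hb subgroup is the only planned Hb-adjusted check of the primary result. Table 6 does name baseline Hb as an example of an outcome-model covariate, but this conflicts with Annex Table 3 and would meet the same missing data. As described, the check confounds a change of population with the addition of Hb, so its agreement or disagreement with the primary estimate cannot be attributed to Hb adjustment.

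It would go too far to say that the most transfused patients all drop out. Total loss follows only from regular transfusion at intervals no longer than the window, and only if a value surviving the wash-out is required for entry. Otherwise they are under-represented. It would also go too far to say that the subgroup can never show the effect of Hb adjustment: a paired fit in the same patients would show it for those patients.

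The size cannot be fixed from the protocol, which does not give the cohort's transfusion distribution. The 2-36% range rests on assumed monthly shares of 5-25%, a proportional effect and four Hb tests per patient. It is smaller than the subgroup's standard error of about 0.70-0.85. The case for change rests on interpretability and low cost, not on a demonstrated large bias.

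**What to change.** 1. In Table 7 and Section 9.9, specify that the primary analysis is fitted twice in the same Hb subgroup, with the PS re-fitted once without and once with mean Hb. Read the effect of Hb adjustment only from that within-subgroup contrast.
2. Report the subgroup's baseline transfusion counts by arm beside those of the full cohort.
3. Reconcile the Table 4 footnote with the Hb value entry in Annex Table 1 on whether the wash-out governs subgroup entry, and fix the window to one length and direction.
4. Keep the wash-out as the main Hb definition, since it has a plain measurement purpose. A definition without it is at most an optional sensitivity analysis, because it trades selection for noisier Hb values.

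The cost is some wording, one descriptive table and one extra model fit on data already held. The limitation that remains is that the contrast speaks only for patients with usable Hb, not for the most frequently transfused, and the report should say so.

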Table 5. Description of Endpoints and Alignment to Study Objectives

Endpoint	Assessment Period	Output	Objective Alignment
Change in RBC transfusions	[Baseline]; [Follow-up]	Mean change in the number of RBC transfusions (maximum 1 per day) PPPY from baseline to follow-up	Primary Objective
VOCs	[Baseline]; [Follow-up]	Mean change in the number of events (maximum 1 per day) PPPY from baseline to follow-up. VOC events need to occur more than 5 days apart to be considered separate events.	Exploratory Objective 1.1
ACS	[Baseline]; [Follow-up]	Mean change in the number of events (maximum 1 per day) PPPY from baseline to follow-up	Exploratory Objective 1.1
ACS Including Pneumonia	[Baseline]; [Follow-up]	Mean change in the number of events (maximum 1 per day) PPPY from baseline to follow-up	Exploratory Objective 1.1
Priapism	[Baseline]; [Follow-up]	Mean change in the number of events (maximum 1 per day) PPPY from baseline to follow-up	Exploratory Objective 1.1

Voxelotor

V2.0 23 December 2024		9	
Stroke (including transient ischemic attack)	[Follow-up]	Time to event during follow-up	Exploratory Objective 1.2
RBC transfusions in follow-up	[Follow-up]	Mean number of RBC transfusions (maximum 1 per day) PPPY in follow-up	Exploratory Objective 2
Percent reduction in RBC transfusion > 30%	[Baseline]; [Follow-up]	Proportion of patients with a percentage decrease in the number of RBC transfusions (maximum 1 per day) PPPY from baseline to follow-up that is greater than 30%	Exploratory Objective 2
Zero RBC transfusions in follow-up	[Follow-up]	Proportion of patients with 0 RBC transfusions (maximum 1 per day) PPPY during follow- up	Exploratory Objective 2
Iron overload	[Follow-up]	Time to event during follow-up	Exploratory Objective 3
Iron chelation use	[Follow-up]	Time to event during follow-up	Exploratory Objective 3
Delayed hemolytic transfusion reactions	[Follow-up]	Time to event during follow-up	Exploratory Objective 3
Alloimmunization	[Follow-up]	Time to event during follow-up	Exploratory Objective 3
Composite outcome (iron overload, iron chelation use, delayed hemolytic transfusion reactions, and/or alloimmunization)	[Follow-up]	Time to event during follow-up	Exploratory Objective 3

Abbreviations: ACS: Acute Chest Syndrome; PPPY: per patient per year; RBC: Red blood cell; VOC: vaso-occlusive crisis The table above includes a summary of the outcomes of interest for this analysis. Operational definitions can be found in the data analysis plan (Section 9.7).

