For sensitivity analysis, transformations of the outcome may also be considered as appropriate. The outcome data will only be viewed overall prior to selecting a method of regression. 95% CI will be reported for the difference between the groups. Full details will be provided in the SAP.

Exploratory Objective 1 – SCD-related Complications Exploratory Objective 1.1 – Change in SCD-related Complications PPPY

VOCs, ACS, ACS + pneumonia, and priapism will be assessed as the change in the rate of events PPPY from baseline to follow-up. For each individual, the rate of each clinical outcome will be calculated as the number of events divided by the number of person-days. The change will be calculated as:

$$Change = \left(\frac{Number\ of\ events\ in\ follow-up}{Available\ days\ of\ follow-up} - \frac{Number\ of\ events\ in\ baseline}{365\ days\ *}\right)x\ 365$$
*All patients have 365 days of baseline data

The change in number of events PPPY will be analyzed using GLM with an identity link to estimate the difference in clinical outcome change rates between the two groups. If any preindex covariates that are found to be unbalanced after the PS method, it will be included in the regression as a covariate. The rate change and its 95% CI will be reported.

Exploratory Objective 1.2 – Time to Stroke

Stroke will be assessed as a time-to-event outcome. Cox proportional hazards (PH) models will be used to calculate the hazard ratio (HR); 95% CIs will be calculated using a robust variance estimator.

Exploratory Objective 2, Endpoint 1 – Number of RBC Transfusions PPPY in Follow-Up

The number of RBC transfusions that occur during the follow-up period will be assessed PPPY during available follow-up within each group. The mean number of RBC transfusions PPPY will be reported for each group. The mean difference between the groups will be assessed using a GLM similar to the primary analysis. The 95% CI will be reported for the difference between the groups.

Exploratory Objective 2, Endpoint 2 – Proportion of Patients with > 30% Reduction in RBC Transfusions

^{*}All patients have 365 days of baseline data

This outcome will be defined as the proportion of patients with a percent reduction in RBC transfusions between baseline and follow-up that is greater than 30%. For each patient, the percent change will be calculated as follows:

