ANNEX 2. ADDITIONAL INFORMATION

Annex Table 1. Covariate and Outcome Operational Definitions

Code lists will be included in SAP document.

Variables	Operational Definition ¹			
Demographic Variables	Demographic Variables			
Age	Age in years (continuous)			
Sex	Sex (categorical) • Male • Female • Unknown • Missing			

V2.0 23 December 2024		
Race	Race/Ethnicity (categorical) White Black or African American Asian or Pacific Islander Hispanic or Latino Other Missing	
Insurance Type	Insurance (categorical)	
Region	Region, based on Census geographic regions (categorical) Northeast Midwest South West Missing	
Top 10 Diagnosing Provider Specialty	Top 10 provider specialties present on the same claim as a SCD diagnosis • To be determined, pending data explorations	
SCD Hematology Diagnosing Provider	Categorical record of a medical claim with a hematologist provider, assessed as the value present on the same claims as an SCD diagnosis, • Yes • No (includes non-hematology and null values)	
SCD Genotype ¹	Genotype (categorical) • Homozygous SS • HSC • HbSB0 thalassemia • HbSB+ thalassemia • Unknown/Other	
SCD Comorbidities		
Acute Chest Syndrome	Presence of an ICD-10-Clinical Modification (CM) diagnosis code on any claim	
Acute Chest Syndrome + Pneumonia	Presence of an ICD-10-CM diagnosis code on any claim for the following conditions: Acute chest syndrome,	

V2.0 23 December 2024		
	AND Pneumonia	
Acute Coronary Syndrome	Presence of an ICD-10-CM diagnosis code on any claim	
Acute Osteomyelitis	Presence of an ICD-10-CM diagnosis code on any claim	
Acute Renal Failure	Presence of an ICD-10-CM diagnosis code on any claim	
Aplastic Crisis	Presence of an ICD-10-CM diagnosis code on any claim	
Intracerebral And Subarachnoid Hemorrhage	Presence of an ICD-10-CM diagnosis code on any claim	
Myocardial Infarction	Presence of an ICD-10-CM diagnosis code on any claim	
Priapism	Presence of an ICD-10-CM diagnosis code on any claim	
Splenic Sequestration Crisis	Presence of an ICD-10-CM diagnosis code on any claim	
Transfusion- Associated Reaction	Presence of an ICD-10-CM diagnosis code on any claim	
Vaso-Occlusive Crisis (VOC)	Definition 1 (primary analysis, strict definition): • Presence of ICD-10 diagnoses code for SCD with VOC (D57.09, D57.21, D57.41, D57.43, D57.45, D57.81) or dactylitis (D57.04, D57.214, D57.414, D57.434, D57.454, D57.814) on a claim from one of the following healthcare settings: • Urgent care visit • Emergency visit • Inpatient visit	

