The Le Broomeer Lear	
VOCs	For each patient, the number of VOCs will be evaluated PPPY in baseline and follow-up.
	See covariate definition above for operational definition and Table 5 for output definition.
ACS	For each patient, the number of events will be evaluated PPPY in baseline and follow-up. See covariate definition above for operational definition and Table 5 for output definition.
ACS Including Pneumonia	For each patient, the number of events will be evaluated PPPY in baseline and follow-up. See covariate definition above for operational definition and Table 5 for output definition.
Priapism	For each patient, the number of events will be evaluated PPPY in baseline and follow-up. See covariate definition above for operational definition and Table 5 for output definition.
Iron overload	For each patient, iron overload will be evaluated as the time to event in days. See covariate definition above for operational definition and Table 5 for output definition.
Iron chelation use	For each patient, iron chelation will be evaluated as the time to event in days. See covariate definition above for operational definition and Table 5 for output definition.
Delayed hemolytic transfusion reactions Alloimmunization	For each patient, DHTR will be evaluated as the time to event in days. See covariate definition above for operational definition and Table 5 for output definition.
Composite outcome (iron overload, iron chelation use, Delayed hemolytic transfusion reactions, and/or alloimmunization)	For each patient, the composite outcome will be evaluated as the time to event (the first of any) in days. See covariate definition above for operational definition and Table 5 for output definition.

Diagnosis (ICD), procedure (ICD, CPT, HCPCS), and drug codes (NDC) or generic names will be documented in the code list accompanying the statistical analysis plan.

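### ACS and priapism are counted as coded claim-days without the episode rule given to VOC, so one episode can count as several events; priapism is also averaged over women

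*Protocol*

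**What the plan says.** All of this is in the protocol.

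- **Counting unit (Section 9.3, Table 5).** ACS, ACS including pneumonia and priapism each have the output "Mean change in the number of events (maximum 1 per day) PPPY from baseline to follow-up". The VOC row has the same output and one further sentence: "VOC events need to occur more than 5 days apart to be considered separate events". No other row has that sentence.
- **What qualifies (Annex Table 1).** ACS is "Presence of an ICD-10-Clinical Modification (CM) diagnosis code on any claim" and priapism is "Presence of an ICD-10-CM diagnosis code on any claim". ACS with pneumonia requires codes for both conditions, again on any claim. VOC under the primary (strict) definition must appear "on a claim from one of the following healthcare settings", namely urgent care, emergency or inpatient.
- **Patient-level outcome (Annex Table 1).** For ACS, ACS including pneumonia and priapism: "For each patient, the number of events will be evaluated PPPY in baseline and follow-up". The entries then refer back to the covariate definition and to Table 5.
- **Analysis (Section 9.7.3).** "VOCs, ACS, ACS + pneumonia, and priapism will be assessed as the change in the rate of events PPPY from baseline to follow-up". The calculation is: "For each individual, the rate of each clinical outcome will be calculated as the number of events divided by the number of person-days". The change is compared by a GLM with identity link. The section adds no episode rule for ACS or priapism and no restriction to males.

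**The concern.** The annex entry for ACS and priapism is a yes/no flag that also serves as a baseline comorbidity. A code on any claim suits a flag. When the same entry is turned into a count capped at one per day, the count is of days bearing a code. Section 9.9 justifies the daily cap for transfusions, because several claims on one day cannot be separated into units or procedures. That reasoning does not carry over to a complication that may last several days and be coded again at follow-up visits.

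Two consequences follow. First, the result is labelled as events per patient per year but depends on how long a stay lasted and how often it was re-coded. A difference between arms in either could look like a difference in complication rate. Second, Section 9.1 says that a fall in transfusions is clinically meaningful only if what transfusions achieve is not lost. Section 9.1 does not name ACS or priapism as that check, but their change scores are among the few results that bear on it.

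Priapism raises a separate matter of interpretation. Women are eligible, cannot have the event, and enter the mean as zeros.

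**Working it through.** The protocol states no rate, SD or power for ACS or priapism, so there is no figure to reproduce. The check applies the written rule to simple cases.

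**Inputs from the protocol.** Daily cap and VOC-only gap rule: Table 5. Any-claim ascertainment: Annex Table 1. Physician and facility claims are both in the data: Section 9.4. Required post-index enrolment of 180 days: Table 2. Both sexes eligible: sex is a covariate in Table 4, and pregnancy is an exclusion in Table 3.

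**Assumptions.** Number of coded days per episode and male share; the documents give neither.

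**1. One episode with the code on L consecutive days.** Events as written = number of distinct coded days = L. PPPY = count / days of follow-up x 365.

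| Coded days L | Events as written | Gap rule, from last coded day | Gap rule, from first coded day | PPPY as written, 365 days | PPPY as written, 180 days |
|---|---|---|---|---|---|
| 1 | 1 | 1 | 1 | 1.0 | 2.0 |
| 3 | 3 | 1 | 1 | 3.0 | 6.1 |
| 5 | 5 | 1 | 1 | 5.0 | 10.1 |
| 7 | 7 | 1 | 2 | 7.0 | 14.2 |
| 10 | 10 | 1 | 2 | 10.0 | 20.3 |

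Example: 10 / 180 x 365 = 20.3, against 1 / 180 x 365 = 2.0 for a single episode. The first row matters: a stay with the code on one date counts once under every rule.

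**2. Effect on the change score.** Take one episode in each year, coded on 7 days at baseline and on 3 days in a full 365-day follow-up. As written the change is 3 - 7 = -4 PPPY. By episodes it is 1 - 1 = 0.

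**3. Effect on precision.** If every episode had the same number of coded days, the mean and the SD would scale together and the test would be unchanged. The loss comes from variation in coded days. With Poisson episodes and independent coded days K per episode (assumption), the variance relative to the squared mean rises by E[K²] / E[K]². With K equally likely to be 1, 3, 5, 7 or 10:

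- E[K] = 26 / 5 = 5.2
- E[K²] = 184 / 5 = 36.8
- ratio = 36.8 / 27.04 = 1.36

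This is an illustration, not an estimate for this cohort.

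**4. Consistency with VOC.** The broad VOC definition in Annex Table 1 includes ACS and priapism as components, and Table 5 does not exempt it from the gap rule. A 7-day ACS stay then gives 1 broad VOC (2 if the gap runs from the first coded day) but 7 ACS events. The component exceeds the composite that contains it.

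**5. Priapism.** All-patient mean = male share x mean in men. With a difference of -0.50 PPPY in men (assumption):

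- 40% male in both arms: 0.40 x (-0.50) = -0.20
- 60% male in both arms: 0.60 x (-0.50) = -0.30
- 55% against 45% male, with the same change of -0.50 in men in both arms: -0.275 - (-0.225) = -0.05

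With equal male shares, including women shrinks a real difference and creates none. Only a sex imbalance produces a spurious one, and in this example it is small.

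**The case against.** The case against has several sound parts.

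- **The cap is a maximum.** The protocol does not say how an inpatient stay is dated or whether professional claims within it count separately. A reader might infer that every admission becomes several events. The text does not support that: inflation occurs only where claims carry the code on several dates. This stands.
- **The rule is common to both arms and both periods.** A reader might infer that the treatment contrast is biased. That would need a difference in length of stay or re-coding, and nothing in the protocol shows one. This stands; what remains is mislabelling, added variance and exposure to such a difference.
- **An episode-based count that includes ACS and priapism is already planned.** Section 9.7.3 foresees a sensitivity analysis with alternative VOC definitions. It helps only in part: it pools the components, uses broader settings, and leaves the separate ACS and priapism endpoints as they are.
- **The SAP may settle it.** Code lists are left to the SAP, but the counting unit is already fixed for each endpoint in Table 5. This is a stated rule, not an omitted detail.
- **VOC was singled out for a reason.** Section 9.9 describes VOC as more prone to misclassification in claims. That may explain special treatment of VOC; it does not make a coded day an episode of ACS.
- **Priapism over all patients is a coherent cohort-level quantity.** That is correct. Sex is a listed covariate whose balance is to be checked, so a reader who infers a false difference goes too far. The male-only figure is easier to interpret; the cohort figure is not wrong.
- **An acute-setting restriction has no stated basis for these outcomes** and could drop events managed elsewhere. This stands, so it belongs in a sensitivity analysis.

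**Conclusion.** The point holds for three exploratory endpoints: ACS, ACS including pneumonia and priapism. As written, they count coded claim-days up to one per day, and the episode rule that the same table applies to VOC is missing. An episode coded on several dates can count as several events. The size is unknown: the 3 to 10 events in place of 1 (at most 2) rest on an assumed 3 to 10 coded days, and the priapism scaling rests on an assumed 40-60% male share. No direction of bias is established. The primary endpoint and its sample size are untouched. The change is worth making before outcomes are analysed, because the definitions are inconsistent with each other and the repair is cheap.

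**What to change.** 1. In Table 5 and Annex Table 1, apply the existing VOC gap rule to ACS, ACS including pneumonia and priapism.
2. State which coded day anchors the gap, for example the last coded day, and use the same anchor for VOC. Without this, a stay of 7 or 10 coded days is 1 event or 2 depending on the programmer.
3. In Section 9.7.3, report the change in priapism among males. The all-patient figure may stand beside it if labelled as such.
4. Keep the daily any-claim count, or a restriction to urgent-care, emergency and inpatient claims, as a sensitivity analysis for these outcomes.

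The cost is protocol wording and a change to the outcome code, with no new data. The downside is fewer counted events, possibly a few true recurrences within the gap merged into one, and a smaller sample for priapism.
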